### Sample Size Analysis for Main Effect of Traditional vs Single-Use Devices

Outcome	Instrument	Traditional		Single-Use		Mean Difference (d)	p-value	SD from means and p-value	Analysis			
		Nevi.	patients	Mean	patients				Effect Size = d/SD	N total 2:1 (80%)	N total 2:1 (85%)	N total 2:1 (90%)
Instrument Set-up Time	No	96	36.61	95	33.56	3.050	0.002	6.82	0.447	300	340	400
	Yes	97	39.00	100	35.96	3.040	0.042	10.49	0.290			
	Comb.	193	37.42	195	34.43	2.985		8.66	0.345			
Instrument Cleanup	No	96	16.43	95	13.59	2.840	0.001	5.96	0.476	240	275	320
	Yes	97	24.96	100	20.09	4.870	0.011	13.44	0.362			
	Comb.	193	20.50	195	16.75	3.752		9.72	0.386			
Combined	No	96	53.04	95	47.15	5.890	0.001	12.37	0.476	180	195	225
	Yes	97	63.96	100	56.05	7.910	0.001	16.87	0.469			
	Comb.	193	57.92	195	51.18	6.737		14.63	0.460			
Surgical Episode Time	No	96	100.58	95	97.11	3.470	0.100	14.58	0.238	290	330	385
	Yes	97	128.51	100	119.61	8.900	0.001	18.98	0.469			
	Comb.	193	113.43	195	107.54	5.893		16.79	0.351			

## 5

### **BENEFIT / RISK PROFILE**

#### 5.1 Potential Benefits

Results of this study will be helpful in evaluating the impact of single-use instrumentation versus traditional metal instruments on overall surgical cost reduction and improving mechanical axis alignment improvement when using patient-matched cutting blocks. The study will provide the initial data to understand the health economic impact of the Efficiency single-use instrumentation when using MyKnee® patient-matched cutting blocks.

#### 5.2 Possible Risks

It is not expected that the possible risks will increase with the instrumentation options. All risks are anticipated with total knee replacement surgery and surgery in general. The following risks and discomforts may occur and are considered anticipated in connection with total knee arthroplasty procedures at the time of the operation:

- Complication from Anesthesia
- Immunologic Response
- Vascular Damage
- Allergic Reaction
- Deep Vein Thrombosis
- Nerve Damage
- Hemorrhage (Bleeding)
- Pulmonary Embolism
- Fat Emboli Syndrome

The following risks and discomforts may occur with reusable or single-use instrumentation:

- Instrument Breakage
- Retention of foreign body
- Instrument Malfunction

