#### **Secondary Objectives:**

To compare the following surgical and clinical outcomes between the two study groups

- To compare correction of alignment after total knee replacement via long standing AP hip-knee-ankle x-rays.
- To compare the accuracy of tibial slope angle on a lateral knee x-ray
- To compare the number of trays sent to sterilization
- To compare the volume of estimated blood loss during the procedure
- To compare the drop in post-operative (day 1) hemoglobin and total volume of transfusions (allogeneic and/or autologous)
- To compare the occurrence of adverse events
- To compare the waste weight at the end of each surgery, considering separately those recyclable and those not recyclable.
- To compare the rate of intraoperative and post-operative complications
- To compare the rate of successful use of MyKnee® cutting blocks (i.e. the incidence of surgical cases where the surgeon did not need to abort the use of MyKnee intra-operatively and default to the use of standard cutting blocks).

The cost-per-minute value based on hospital estimates will be used to calculate an overall cost-savings total.

## 2

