### Additional Operative Parameters

1. Estimated blood loss (cc)
2. Drop in post-operative hemoglobin (measured at Day 1 or discharge if patient does not stay overnight)
3. Total volume of transfusions (allogeneic and/or autologous)
4. Number of trays sent to sterilization
5. Waste weight at the end of each surgery; recyclable and non-recyclable (grams)

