### 6.1 Adverse Event Definition

An adverse event (AE) is any symptom, sign, illness or experience that develops or worsens in severity during the course of the study. Intercurrent illnesses or injuries should be regarded as adverse events. For the purposes of this study, AE's will include any complications that may be routinely observed with total knee arthroplasty, such as infection, prosthesis loosening, etc. AE's will be noted within the research database whenever the Investigator is aware of them.

Adverse event collection will begin from the time of first incision. All medical events and conditions that occur prior to this time point are to be captured as pre-existing conditions in the patient's medical history. Adverse event collection will conclude at the completion of the final follow-up visit.

*Observed and reported adverse* events shall be recorded in the patient's study records and on the Adverse Event Form within 48 hours of the site becoming aware of each event, and must include the following information at minimum:

- Event Description
- Date of Onset
- Date of Resolution
- Severity (mild, moderate, severe)
- Seriousness
- Relationship to surgery (definitely, probably, possibly, unlikely, not related)
- Relationship to instrumentation (definite, probable, possible, unlikely, not related)
- Event treatment (e.g., none, non-drug therapy, medications, surgery)
- Outcome

Significant new information and updates will continue to be captured in the patient's records as they become available. The investigator will follow each subject who experiences an AE until the event resolves or no further improvement is expected. If the AE has not resolved by the time of the subject's completion, the AE will be listed as ongoing at the time of subject discontinuation.

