### ***6.3 Relationship to Surgery/Instrumentation***

The investigator will evaluate the relationship of the adverse event to the research intervention according to the following definitions. The term "treatment-related," as it pertains to adverse events, means that the event was or may have been attributable to the treatment, or that the treatment was or may have been a factor in an event, including those occurring as a result of malfunction, poor manufacture, inadequate labeling, or improper design.

- Definitely

The adverse event is clearly related to the research intervention: the adverse event has a temporal relationship to the administration of the research intervention, follows a known pattern of response, or is otherwise logically related to the intervention, and no alternative cause is present.

- Probably

The adverse event is likely related to the research intervention: the adverse event has a temporal relationship to the administration of the research intervention, follows a known or suspected pattern of response, or is otherwise logically related to the intervention, but an alternative cause may be present.

- Possibly

The adverse event may be related to the research intervention: the adverse event has a temporal relationship to the administration of the research intervention, follows a suspected pattern of response, or is otherwise logically related to the intervention, but an alternative cause is present.

- Unlikely

The adverse event is doubtfully related to the research intervention: the adverse event has a temporal or other relationship to the administration of the research intervention, but follows no known or suspected pattern of response, and an alternative cause is present.

- Not Related

The adverse event is clearly NOT related to the research intervention: the adverse event has no temporal or other relationship to the administration of the research intervention, follows no known or suspected pattern of response, and an alternative cause is present.

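### Breakage, malfunction and retained fragments are the named instrument risks, but no listed data item records them in either arm, so the safety comparison will not capture them reliably or uniformly

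*Combined protocol and SAP*

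**What the plan says.** - **Risks.** Section 5.2 states "The following risks and discomforts may occur with reusable or single-use instrumentation" and lists three: instrument breakage, a retained foreign body and instrument malfunction. The other risks in that section are attributed to knee replacement or to surgery in general.
- **Operative data.** Section 3.3 lists times by phase, starting with bringing instruments from stock and preparing the table. It then lists five further parameters: blood loss, hemoglobin drop, transfusion volume, "Number of trays sent to sterilization" and waste weight. Section 3.4 and its schedule add no item on instrument failure.
- **Adverse events.** Section 6.1 defines an adverse event as "any symptom, sign, illness or experience that develops or worsens in severity during the course of the study" and adds that "AE's will include any complications that may be routinely observed with total knee arthroplasty, such as infection, prosthesis loosening, etc". It also states "Adverse event collection will begin from the time of first incision".
- **Attribution.** Each recorded adverse event is graded for its relationship to the instrumentation. Section 6.3 extends treatment-related events to those "including those occurring as a result of malfunction, poor manufacture, inadequate labeling, or improper design".
- **Objectives.** Section 1.3 lists adverse events and, separately, "To compare the rate of intraoperative and post-operative complications". It also lists the rate at which the MyKnee blocks were used without being abandoned.
- **Analysis.** Section 4 plans a non-inferiority evaluation that includes the adverse-event rate, with no margin given.

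**The concern.** The arms differ in their instruments and technique, and the three risks in section 5.2 are the ones tied to the instruments. One would expect the trial to count them in both arms. Instead, the lists of data to be collected leave them out. Their only routes into the data are general ones: an adverse-event definition with clinical examples, and a complication rate that is never defined.

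The safety conclusion is at stake. If harmless failures are recorded at some sites and not at others, or more readily in one arm, the trial could report similar adverse-event rates while instrument reliability differs. A brief failure during surgery that nobody wrote down cannot be reliably reconstructed afterwards.

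**Working it through.** **1. Follow each kind of failure through the text.**

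| Failure | Route into the data | Gap |
|---|---|---|
| Fault found while preparing instruments or table | None listed | The phase is timed (3.3), but adverse-event collection starts at first incision (6.1) |
| Instrument cracks or malfunctions, is replaced, patient unaffected | Perhaps an *experience* (6.1) or an intraoperative complication (1.3) | No data item; complication undefined; severity in 6.2 is graded by symptoms, daily activities and need for therapy, which do not fit |
| Fragment retained | Readily an operative adverse event (3.3) or a complication (1.3) | No required item, so it depends on the site's reading |
| MyKnee blocks abandoned | Success-rate objective (1.3) | Group A only; omits other Efficiency instruments and everything in Group B |
| Serious, unanticipated device problem | Section 6.5 | Does not reach non-serious failures |

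The grading for relationship to instrumentation applies only once an event has been recorded as an adverse event, and 6.3 treats malfunction as a cause of such an event. The deviation categories in 3.2.3 contain none for instrument failure, and replacing an instrument like for like is not a departure from the assigned arm.

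**2. The plan's own figure.** The sample size in 4.2 rests on instrument set-up time: difference 2.985, SD 8.66, 2:1 allocation, 80% power, alpha 0.05 (two-sided assumed).

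Group B n = 1.5 × (1.960 + 0.842)² × (8.66/2.985)² = 1.5 × 7.85 × 8.42 ≈ 99.1, rounded up to 100. The total is then 300, and 300 × 1.14 = 342 (228:114). This reproduces the plan. It sizes a time endpoint only and says nothing about failures.

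**3. What incomplete capture does.** The documents give no failure rate, so the rates below are assumptions. With true rate p in Group A and a fraction h recorded, expected records are 228 × p × h, and the chance of at least one is 1 − (1 − p·h)^228.

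| p | h | Expected records | Chance of at least one |
|---|---|---|---|
| 1% | 100% | 2.3 | 90% |
| 2% | 100% | 4.6 | 99% |
| 2% | 50% | 2.3 | 90% |
| 2% | 25% | 1.1 | 68% |
| 2% | 10% | 0.5 | 37% |
| 5% | 100% | 11.4 | >99.9% |

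Randomization is done separately for each site, so a site that under-records equally in both arms mainly lowers the counts. Bias comes from recording that differs by arm. For example, true rates of 2% and 1% recorded at 25% and 50% give 0.02 × 0.25 = 0.5% and 0.01 × 0.50 = 0.5%, an apparent tie. The direction of any such bias is unknown.

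**4. What complete capture would allow.** With zero events, the one-sided 95% upper bound is 1 − 0.05^(1/n):

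- n = 228: 1.3%; n = 114: 2.6%
- n = 200: 1.5%; n = 100: 3.0% (if only the 300 minimum is reached)

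Power for a between-arm test at 228:114 is Φ[(|pA − pB| − 1.96·SE0)/SE1], where SE0 uses the pooled rate and SE1 the separate rates. For 2% against 1%, the pooled rate is (4.56 + 1.14)/342 = 1.67%, SE0 = 0.01469 and SE1 = 0.01315. That gives Φ[(0.01 − 0.0288)/0.01315] = Φ(−1.43) ≈ 8%.

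Against 1% in Group B, Group A rates of 3%, 5% and 8% give 17%, 45% and 81%. With about one expected event in Group B the approximation is rough, and these are orders of magnitude only.

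**The case against.** The strongest reply is that the plan already has routes for these events. The adverse-event definition is not limited in words to harm, and *experience* is broad. Section 3.3 requires operative adverse events observed by the investigator to be recorded, and assessment is scheduled at the operative and 6-week visits, so reporting is not merely spontaneous. The complication-rate objective applies to both arms, and a retained fragment fits it easily. If a retained fragment needed intervention to prevent permanent damage, it would be a serious adverse event under 6.4. The case report form is not in the documents and may already have a field. Section 7.2 commits the trial to ISO 14155, whose content cannot be checked here.

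Much of this stands. A reader might infer that failures go uncounted unless the patient is harmed. The text does not say so, and the routes above contradict it as a rule. A reader might also infer that failures blur the time endpoints. They do not: time lost to a failed instrument is part of that instrument system's effect and belongs in the randomized comparison. Nor do the documents show that breakage is the main device risk. Section 5.2 expects no added risk from the instrumentation options, and section 1.2 describes the polymer as resistant to fatigue and abrasion.

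The reply does not supply a definition of intraoperative complication, a matching data item, or a both-arm count of failures. If a form field exists, the protocol should name it and plan its reporting.

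**Conclusion.** The point holds in a limited form. The plan names three instrument risks, lists no data item for them in either arm, and leaves their capture to an undefined term applied site by site. The plan describes no blinding, and the operating surgeon necessarily knows which instruments are in use. The safety comparison therefore does not reliably or uniformly capture instrument failures; it cannot be said to miss them altogether.

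The size cannot be fixed from the documents. At an assumed 2% in Group A, about 4.6 failures would be expected, and between about 0.5 and 4.6 would be recorded as capture runs from 10% to 100%. Even full capture would not support a formal test for rare failures. It would support a useful upper bound in each arm. The conclusion rests on the listed data items being complete, since the forms were not available. This is a cheap improvement; the primary time comparison and the sample size are unaffected.

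**What to change.** 1. Add to Additional Operative Parameters in section 3.3, for every case in both arms and from instrument preparation onward, required yes/no items: instrument breakage; instrument malfunction; fragment retained or retrieved; instrument replaced or back-up set opened (with instrument type). Complete them whether or not an adverse event follows.
2. Define intraoperative complication for the section 1.3 objective, and state whether these items count toward it.
3. In section 4.1, report the items by arm, separately from adverse events, as counts and percentages with exact confidence intervals for each arm and for the difference. Label the comparison descriptive.

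No change to sample size, visits, treatment or safety-reporting deadlines is needed. The cost is a few tick-boxes on operative data already collected for each case, and one table. The downside is slightly more form-filling and a count that may be less favorable to the single-use arm.

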### 6.1 Adverse Event Definition

An adverse event (AE) is any symptom, sign, illness or experience that develops or worsens in severity during the course of the study. Intercurrent illnesses or injuries should be regarded as adverse events. For the purposes of this study, AE's will include any complications that may be routinely observed with total knee arthroplasty, such as infection, prosthesis loosening, etc. AE's will be noted within the research database whenever the Investigator is aware of them.

Adverse event collection will begin from the time of first incision. All medical events and conditions that occur prior to this time point are to be captured as pre-existing conditions in the patient's medical history. Adverse event collection will conclude at the completion of the final follow-up visit.

*Observed and reported adverse* events shall be recorded in the patient's study records and on the Adverse Event Form within 48 hours of the site becoming aware of each event, and must include the following information at minimum:

- Event Description
- Date of Onset
- Date of Resolution
- Severity (mild, moderate, severe)
- Seriousness
- Relationship to surgery (definitely, probably, possibly, unlikely, not related)
- Relationship to instrumentation (definite, probable, possible, unlikely, not related)
- Event treatment (e.g., none, non-drug therapy, medications, surgery)
- Outcome

Significant new information and updates will continue to be captured in the patient's records as they become available. The investigator will follow each subject who experiences an AE until the event resolves or no further improvement is expected. If the AE has not resolved by the time of the subject's completion, the AE will be listed as ongoing at the time of subject discontinuation.

### 6.2 Assessment of Severity

The severity of the adverse event is classified as mild, moderate or severe.

- Mild: Awareness of signs or symptoms, but easily tolerated and are of minor irritant type causing no loss of time from normal activities. Symptoms do not require therapy or a medical evaluation; signs and symptoms are transient.
- Moderate: Events introduce a low level of inconvenience or concern to the participant and may interfere with daily activities, but are usually improved by simple therapeutic measures; moderate experiences may cause some interference with functioning.
- Severe: Events interrupt the participant's normal daily activities and generally require systemic drug therapy or other treatment; they are usually incapacitating.

### ***6.3 Relationship to Surgery/Instrumentation***

The investigator will evaluate the relationship of the adverse event to the research intervention according to the following definitions. The term "treatment-related," as it pertains to adverse events, means that the event was or may have been attributable to the treatment, or that the treatment was or may have been a factor in an event, including those occurring as a result of malfunction, poor manufacture, inadequate labeling, or improper design.

- Definitely

The adverse event is clearly related to the research intervention: the adverse event has a temporal relationship to the administration of the research intervention, follows a known pattern of response, or is otherwise logically related to the intervention, and no alternative cause is present.

- Probably

The adverse event is likely related to the research intervention: the adverse event has a temporal relationship to the administration of the research intervention, follows a known or suspected pattern of response, or is otherwise logically related to the intervention, but an alternative cause may be present.

- Possibly

The adverse event may be related to the research intervention: the adverse event has a temporal relationship to the administration of the research intervention, follows a suspected pattern of response, or is otherwise logically related to the intervention, but an alternative cause is present.

- Unlikely

The adverse event is doubtfully related to the research intervention: the adverse event has a temporal or other relationship to the administration of the research intervention, but follows no known or suspected pattern of response, and an alternative cause is present.

- Not Related

The adverse event is clearly NOT related to the research intervention: the adverse event has no temporal or other relationship to the administration of the research intervention, follows no known or suspected pattern of response, and an alternative cause is present.

### ***6.4 Serious Adverse Events***

A serious adverse event (SAE) is any adverse event that:

- Results in death;
- Is life-threatening; the subject was at substantial risk of dying at the time of the adverse event, or use or continued use of the device or other medical product might have resulted in the death of the patient;
- Results in hospitalization (initial or prolonged);
- Results in disability or permanent damage; the event resulted in a substantial disruption of the person's ability to conduct normal life functions;
- Results in a congenital anomaly or birth defect;

- Requires intervention to prevent permanent impairment or damage; medical or surgical intervention was necessary to preclude permanent impairment of a body function, or prevent permanent damage to a body structure.
- Results in any other serious, important medical events; the event does not fit the other outcomes, but the event may jeopardize the patient and may require medical or surgical intervention to prevent one of the other outcomes.

In case of Serious Adverse Events (SAE), the Investigator must notify the Sponsor or its representative using the Adverse Event Form as soon as possible but at most within 24 hours **of** becoming aware of the event using the contact information below.

Sponsor Contact: [name]

E-mail: [[contact]](mailto:[contact])

[contact]

The Investigator should provide additional information on the SAE by updating the information on the Adverse Event Form and CRF as updates become available. The Sponsor may also ask for additional clinical reports including redacted source documents to be provided by the Investigator to assist in the assessment of the event. Significant new information and updates should continue to be submitted promptly to the Sponsor and entered on the Adverse Event CRF as they become available, and the Investigator should follow the SAE until it is resolved or no further improvement is expected.

New SAEs will only be documented for each patient until the last study-related clinic visit.

### 6.5 *Unanticipated Adverse Device Effects*

An UADE is defined as any serious adverse effect on health or safety or any life-threatening problem or death caused by, or associated with, a device/product, if that effect, problem, or death was not previously identified in nature, severity, or degree of incidence in the protocol or application, or any other unanticipated serious problem associated with a device/product that is related to the rights, safety, or welfare of subject. Adverse events that might reasonably occur because of placement or attempted placement of the product or during follow-up are identified through a risk assessment and summarized in the Instructions for Use.

If Medacta determines that a UADE presents an *unreasonable risk* to study subjects, Medacta will:

- terminate the investigation, or the parts of the investigation presenting that risk, within 5 working days after making the “unreasonable risk” determination, or within 15 working days of receiving notice of the UADE
- immediately investigate and evaluate the adverse effect,
- report the results of the investigation to all reviewing IRBs and to all participating investigators within 10 working days after Medacta receiving notice of the UADE, and
- resume the study, if appropriate, as specified by the IRB.

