# **7**

## **ETHICAL AND LEGAL ASPECTS**

### **7.1 Institutional Review Board (IRB)**

This trial can only be undertaken after full approval has been obtained through the IRB or Ethics Committee (EC). The approval(s) must cover the protocol and addenda, if applicable, as well as the Informed Consent Form, product brochure and manufacturer information (if applicable).

During the trial the following documents will be sent to the EC/IRB for their review:

- Changes to the product brochure and manufacturer information
- Reports of all Adverse Events that are rated serious, unexpected and associated with the study product and meet IRB reporting requirements.
- All protocol amendments and revised Informed Consent Forms (if any).

For any protocol amendments that increase subject risk, the amendment and applicable Informed Consent Form revisions must promptly be submitted to the EC/IRB for review and approval prior to implementation of the change(s).

Reports on, and reviews of the trial and its progress will be submitted to the EC/IRB by the Investigator at intervals stipulated in their guidelines.

At the end of the trial, the Investigator will notify the EC/IRB about the trial completion.

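### Section 6.5 requires the sponsor to investigate an unanticipated adverse device effect (UADE) and report it to all sites only after an unreasonable-risk finding, and its clocks start from different events

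*Combined protocol and SAP*

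**What the plan says.** Section 6.5 defines a UADE and then gives the sponsor four actions, all introduced by one conditional sentence: "If Medacta determines that a UADE presents an" unreasonable risk to study subjects. The actions are:

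- to terminate all or part of the investigation, either "within 5 working days after making the" determination, "or within 15 working days of receiving notice of the UADE";
- to "immediately investigate and evaluate the adverse effect";
- to "report the results of the investigation to all reviewing IRBs and to all participating investigators"; the time limit set for this report is "within 10 working days after Medacta receiving notice of the UADE";
- to resume the study, where appropriate, as the IRB specifies.

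No other sentence in 6.5 assigns the sponsor an action. Outside it, section 7.1 sends to the EC/IRB "Reports of all Adverse Events that are rated serious, unexpected and associated with the study product and meet IRB reporting requirements". Section 6.6 leaves adverse event reporting to each overseeing board's own requirements. Section 6.4 has the investigator notify the sponsor of a serious adverse event (SAE) within 24 hours and allows the sponsor to request further reports.

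**The concern.** An investigation normally supplies the evidence for deciding whether a risk is unreasonable. In 6.5 the order is reversed: the duty to investigate arises only once that decision has been made. The duty to inform every site hangs on the same decision, although its clock starts earlier, at notice.

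This matters because the trial is multi-center, 228 patients are allocated to the single-use instruments with patient-specific blocks (section 3), and the single-use instruments arrive pre-sterilized from one manufacturer (sections 1.1 and 1.2). A device problem seen at one site could be relevant at the others. Followed to the letter, the protocol would let those sites continue without being told of a UADE that the sponsor had not classed as an unreasonable risk. Section 3.2.3 makes SAE/UADE reporting a protocol-deviation category, so the wording is also what compliance is judged against.

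**Working it through.** The plan states no figure on this point to reproduce. The check has two parts.

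**1. What is required for a UADE not judged an unreasonable risk**

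| Section | What it provides without the condition | Sponsor evaluation required? | Notice to other sites' investigators required? |
|---|---|---|---|
| 3.2.1 | Subjects are told of relevant new information | No | No |
| 6.1 | Site records each event within 48 hours, with relationship to instrumentation | No | No |
| 6.3 | Investigator rates causality | No (investigator only) | No |
| 6.4 | SAE notified to the sponsor within 24 hours; sponsor may request reports to help assess it | No (discretionary, no deadline) | No |
| 6.6 | Reporting to the overseeing IRB under its own rules | No | No |
| 7.1 | Serious, unexpected, product-associated events go to the EC/IRB if they meet its requirements | No | No |

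The UADE definition also covers serious problems that touch subjects' rights or welfare. Such a problem may meet none of the SAE criteria in 6.4, in which case the 24-hour route would not apply either.

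**2. The clocks**

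Count working days from notice (day 0) and let the determination fall on day D. Section 6.5 sets no limit on D; the values below are illustrative.

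- Termination limit counted from determination: D + 5.
- Termination limit counted from notice: 15.
- Days left for the results report once its trigger exists: 10 − D.

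| D | D + 5 | Limit from notice | Difference between limits | 10 − D |
|---|---|---|---|---|
| 0 | 5 | 15 | 10 | 10 |
| 2 | 7 | 15 | 8 | 8 |
| 5 | 10 | 15 | 5 | 5 |
| 10 | 15 | 15 | 0 | 0 |
| 12 | 17 | 15 | 2 | −2 |
| 14 | 19 | 15 | 4 | −4 |

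The termination limits agree only when D + 5 = 15, that is D = 10. Before day 10 the limit from determination is the earlier; after day 10 the limit from notice is. At D = 10 no time is left to investigate before the report is due. At D = 14 the report was due 4 working days before the duty to make it arose. For D below 10, the report and both termination limits can all be met.

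**The case against.** The strongest reply is that the sponsor cannot determine that a risk is unreasonable without first assessing the event. The report clock runs from notice, which suggests that work is meant to start then, and the 24-hour SAE rule in 6.4 presupposes some sponsor assessment. On this view the layout is poor drafting and not a missing duty. It is fair to say that an assessment before the determination is implied. It is nowhere required, however, and a plausible implied assessment does not create a duty to tell other sites about a UADE that falls short of the finding.

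A reader might infer that such a UADE could go wholly unevaluated. The documents do not support that: the investigator's causality rating, SAE notice to the sponsor and IRB reporting all operate without the condition, and the 7.1 category overlaps heavily with the UADE definition.

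A reader might also infer that the deadlines contradict one another, or that the determination may be made as late as day 15. Neither follows. The 10-day limit governs reporting and the 15-day limit governs termination, and they can be met together when the determination comes early. Section 6.5 puts no cap on the determination; the 15 days apply to termination.

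It is also true that the picture of other sites continuing unaware is hypothetical, and that the documents give no expected UADE count.

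**Conclusion.** The point holds as a misplaced condition in a stated safety rule. For a UADE not judged an unreasonable risk, no section requires the sponsor to evaluate it or to tell investigators at the other sites. The partial routes in 6.1, 6.3, 6.4, 6.6 and 7.1 reduce the gap but do not close it.

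The timing defect is narrower: different starting points, no deadline for the determination, and an unexplained choice between two termination limits. It produces an unworkable sequence only when the determination comes on working day 10 or later. On any day other than day 10, the date by which termination is due is ambiguous.

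This rests on reading the introductory condition as governing all four listed actions, which is how the section is laid out. How often it would matter cannot be sized from the documents. The trial's estimates and error rates are not touched. The change should be made because it improves safety oversight and takes little work.

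**What to change.** Reword section 6.5 in three respects.

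1. Take the investigation, and the report to every reviewing IRB and participating investigator, out of the unreasonable-risk condition, so that both run from receipt of notice of any UADE. This keeps the report's existing clock.
2. Leave termination and resumption conditional on the determination.
3. Reconcile the two existing termination limits and state which governs or how they combine. That choice is the sponsor's; no new limit or stopping rule is proposed here.

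Sections 6.4, 6.6 and 7.1 should then be checked for consistency with the revised text.

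The cost is an edit to one section, plus a small amount of added sponsor work for UADEs that turn out not to be judged an unreasonable risk.
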